### Clinical Site Coordination

Drs. [name], [name] and [name] along with [name] from the Michigan Department of Health will provide guidance for the coordination of the clinical sites. Drs. [name] and [name] will visit each site prior to implementation of data collection to introduce the project to staff and discuss issues sites may have. To ensure success, there will be at least weekly meetings with all three site RA and the Research Director, [name]. RAs will provide weekly reports of activities and recruitment. In addition, we will hold monthly teleconference with the research team and the Site PIs to discuss any larger issues and potential adverse events. Consistency among the sites will be monitored with these reports and communication strategies. Research team coordination with communication and meetings is based on the successful accomplishment of previous research project (R01 HD058854).

### Analysis Plan

Summary statistics for baseline demographics (age, ethnicity, race, income, etc.) will be calculated and reported for each intervention group (App or Video) versus Control. We will utilize multilevel generalized mixed modeling (via SPSS and R) under an intent-to-treat (ITT) approach to compare primary, secondary outcomes, and exploratory outcomes.

**Hypothesis Testing:** To evaluate the fixed effect of the two different groups upon knowledge we will utilize a single level model that includes the fixed effect of group (G).

$$Y_i = [\gamma_0 + \gamma_1 G_i] + [\zeta_i + \epsilon_i]$$

where Y is the composite score for knowledge. G is an indicator for the different groups (App or Video, Control). We will set alpha = 0.05. The two group model reduces to a 2 sided, t-test approach.

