## Recruitment

Our research procedures are designed to mirror the current practice at the individual hospitals as much as possible. Typically, nurses discuss the BioTrust informational brochure shortly after moving into the Mother & Baby unit as part of the packet of information related to their stay in the unit. Once the baby is 24 hours old, the nursery tech comes to complete newborn screening and asks for BioTrust consent at that time.

Our approach will use a full time research assistant (RA) at each hospital. All potential participants will receive the brochure as part of standard practice during their welcome to the Mother & Baby Unit. At some point after admission to the Unit, the RA will approach the patient, briefly describe the study and content of data collected, and seek verbal consent for participation in the study. If they consent, the RA will activate the study-provided electronic tablet to see the study group assignment; study staff and healthcare providers will be blind to the study group assignment until this point. Participants will be randomized into the video intervention group (Group A), interactive intervention group (Group B), or standard of care group (Group C). The patient will then complete the intervention (Groups A and B) or continue the BioTrust discussion with the nurse (Group C).

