## Intervention Groups A and B

Following randomization, participants in Groups A or B will be given the electronic tablet with the intervention loaded on the screen and provided with instructions. In order to allow participants as much time as necessary to explore the app, the RA will leave the room while the patient is working on the tablet and return within an hour to pick up the tablet. Participants in Group A will be asked to watch a 6-minute video about what it means to consent to have the NBS bloodspots retained by the Michigan BioTrust. Participants in Group B will be provided with the same information in an interactive app form, and will be asked to explore the informational sections at their preferred level of depth. After the video ends or participants

reach the end point of the educational app, they will automatically be directed to complete the associated questionnaires. When the RA returns, she will collect the tablet and provide the participant with a \$25 gift card to Amazon. The next day, the Nursery Tech will visit the patient's room to gather NBS bloodspots and consent for the BioTrust, following the **standard consent process**.

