### Control Group C

Participants who are randomized to Group C will complete the questionnaires immediately following the BioTrust discussion with the nurse. The RA will stay in the room while the surveys are being completed then provide the participant with a \$25 gift card to Amazon. The next day, the Nursery Tech will visit the patient's room to gather NBS bloodspots and consent for the BioTrust, following the **standard consent process**. The RA will review collected consent cards to document the patient's choice to consent or deny.

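### The knowledge comparison leaves hospital out in a three-site trial; the test stays valid, and adding two hospital indicators is a cheap way to protect precision

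*Combined protocol and SAP*

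**What the plan says.** The Analysis Plan opens with a general commitment: "We will utilize multilevel generalized mixed modeling (via SPSS and R) under an intent-to-treat (ITT) approach". Under its Hypothesis Testing paragraph, knowledge gets a different model: "we will utilize a single level model that includes the fixed effect of group (G"). The equation has an intercept, one group coefficient, and two error terms (zeta and epsilon) that carry the same participant index and are not defined. Of the group variable the plan says "G is an indicator for the different groups (App or Video, Control"), and it adds "The two group model reduces to a 2 sided, t-test approach".

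On sites, the Recruitment section says "Our research procedures are designed to mirror the current practice at the individual hospitals as much as possible" and "Our approach will use a full time research assistant (RA) at each hospital". Clinical Site Coordination refers to three sites. Participants are randomized to video (A), interactive app (B) or standard of care (C). Those in Group C "will complete the questionnaires immediately following the BioTrust discussion with the nurse". Survey Tools describes two surveys per participant, one straight after the intervention or control and one by telephone 2-4 weeks later.

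**The concern.** The three hospitals have different staff and different routines, and the procedures deliberately keep those routines. Group C's knowledge is measured right after a conversation with that hospital's own nurse. Hospital is therefore a plausible source of variation in the score, although the documents do not show how large it is. A model with group alone leaves that variation in the residual, so the confidence interval for the group difference may be wider than it needs to be. The general commitment to multilevel modelling and the single-level model for knowledge also need a sentence that reconciles them.

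**Working it through.** **Inputs from the documents.** Three randomized arms, participants as the unit of randomization (Recruitment); three hospitals, hence two indicators (Clinical Site Coordination); two-sided alpha of 0.05 (Analysis Plan).

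**Assumptions.** The available text gives no sample size, standard deviation or hospital effect. I take total N = 150, 300 and 600, and let hospital explain R² = 0, 1, 5 or 10% of the variance in knowledge. Simulations use equal arms and hospital shares of 45/35/20%. The reference power is 80%.

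**1. The plan's own statement.** On one simulated data set with a binary group variable, the regression p-value and the t-test p-value agree (0.99939 for both), so the t-test sentence is correct for two groups. With one score per person, the log-likelihood is the same (-269.254) whether the variance is split 0.1/0.9, 0.5/0.5 or 0.9/0.1 between zeta and epsilon. The two terms collapse to one residual, and the group estimate is unaffected.

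**2. Validity without hospital.** With 5,000 simulated trials per cell (Monte Carlo standard error 0.003) and simple randomization, type I error is 0.045-0.054 without hospital and 0.044-0.054 with it. If randomization is stratified by hospital, the unadjusted test has type I error 2[1 - Φ(1.960/√(1 - R²))], which is 0.0443 at R² = 5% and 0.0388 at 10%. The simulation gives 0.044 and 0.039, against 0.049 at both with hospital in the model.

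**3. Precision.** For three arms and two added parameters, the standard error with hospital relative to the group-only model is

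ratio = √[(1 - R²)(N - 4)/(N - 6)].

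Example: N = 150, R² = 5% gives √(0.95 × 146/144) = 0.981. A comparison with 80% power then has power Φ(2.802/ratio - 1.960) = Φ(2.802/0.9814 - 1.960) = 81.5%.

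| R² (assumed) | Ratio, N = 150 | N = 300 | N = 600 | Power, starting from 80% |
|---|---|---|---|---|
| 0% | 1.007 | 1.003 | 1.002 | 79.5-79.9% |
| 1% | 1.002 | 0.998 | 0.997 | 79.9-80.3% |
| 5% | 0.981 | 0.978 | 0.976 | 81.5-81.8% |
| 10% | 0.955 | 0.952 | 0.950 | 83.5-83.8% |

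Pooling app and video into one group changes the factor to (N - 3)/(N - 5), and the ratios agree to within 0.0001.

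**4. Break-even.** The ratio equals 1 when R² = 2/(N - 4): 2/146 = 1.4%, 2/296 = 0.7% and 2/596 = 0.3%.

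**5. Hospital effect in Group C only.** If hospital explains 5% or 10% of the variance in Group C and none elsewhere, the simulated ratio for app or video versus control is 1.002 and 0.994 (N = 150), 0.997 and 0.990 (N = 300), 0.996 and 0.992 (N = 600). The gain is about nil.

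**6. Coding of the group variable.** With illustrative means of 0 (control), 0.5 (video) and 0.3 (app), the pooled contrast is (0.5 + 0.3)/2 = 0.40, while the separate contrasts are 0.5 and 0.3. The plan should say which it intends.

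**The case against.** The best case for leaving the plan alone is that this is a choice between two sound analyses. The group-only test is valid, no hospital effect is documented, and every N and R² above is assumed. At R² = 1% the result ranges from a trivial loss to a trivial gain. The reason for expecting a hospital effect also weakens the expected benefit. Local practice mainly reaches Group C through the nurse discussion, whereas Groups A and B receive study-provided tablet content, and in that pattern the gain is about nil. Clinical Site Coordination also provides for monitoring consistency between sites. All of this stands, and it keeps the point minor. It does not remove it, because the downside is bounded and hospital is known for everyone.

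A further objection is that the two modelling statements need not conflict. The plan never says that the levels are hospitals. They could be the two surveys per participant, with a single-level model for one knowledge comparison sitting under the general statement. This also stands: a reader might infer that a hospital term was promised and then dropped, but the text does not support that.

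The group contrast is not wholly open either. The sentence on baseline summaries speaks of each intervention group against control, which favours two separate comparisons. It concerns summaries rather than the test, so it helps without settling the matter.

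**Conclusion.** The concern holds as a minor point of efficiency. Hospital is absent from the knowledge model in a three-site trial, and including it is a low-risk improvement. At an assumed N of 150 to 600, the standard error falls by about 2% if hospital explains 5% of the variance and by about 5% at 10%. It rises by 0.2-0.7% if hospital explains nothing and is practically unchanged if hospital matters only in Group C. The documents do not say which case applies.

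Two stronger readings are tempting. A reader might infer that ignoring hospital inflates the false-positive rate, as it would if hospitals were randomized. Here participants are randomized, so the test keeps its level, or is slightly conservative under stratification. The available text does not describe stratification, and its absence there is not held against the plan. A reader might also infer that the equation cannot be fitted. Once the group variable is binary, the errors reduce to one residual and the t-test sentence is right. The spare error term is clerical, and the group coding and the survey that supplies the score are missing details.

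**What to change.** Specify for the knowledge score a linear model with group and two fixed hospital indicators. Fixed effects are preferable because three sites are too few to estimate a hospital variance. Keep the unadjusted comparison as a sensitivity analysis.

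In the same edit, as wording only:

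- drop zeta and keep one residual, given one score per participant;
- state whether the group variable pools app and video against control (one term) or compares each with control (two terms);
- name the survey that supplies the score;
- say what the levels are in the general multilevel statement.

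If two contrasts are intended, how alpha is shared between them is a separate decision.

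The cost is a few sentences in the Analysis Plan and one added factor in the software already named. No new data and no missing-covariate rule are needed. The statistical price is the two parameters whose worst case is in the R² = 0 row of the table.

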### Survey Tools

All participating women will complete a survey 1) immediately following the intervention/control on the electronic tablet and 2) by telephone 2-4 weeks follow up. Participants will receive an additional \$25 gift card to Amazon after the follow-up survey.

Outcome measures include:

- knowledge of the elements of consent and key aspects of the biobank
- decisional conflict
- satisfaction with the consent process and attitudes toward the clinical program the samples were collected for and research with these samples
- rates of parental permission

We will also collect demographic information on the participants and contact information for contact by telephone 2-4 weeks later. All identifying information will be kept in a secure data storage system separate from data used for analyses.

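### The knowledge model contains group alone, so demographics the trial already collects are described but not used to sharpen the comparison

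*Combined protocol and SAP*

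**What the plan says.** The Analysis Plan gives one explicit model, and it is for knowledge: "we will utilize a single level model that includes the fixed effect of group (G", "where Y is the composite score for knowledge". The equation has an intercept, a group term and residual terms, and nothing else. On testing, the plan says "We will set alpha = 0.05" and "The two group model reduces to a 2 sided, t-test approach".

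Under Survey Tools, participants are to "complete a survey 1) immediately following the intervention/control on the electronic tablet and 2) by telephone 2-4 weeks follow up", and the first outcome listed is "knowledge of the elements of consent and key aspects of the biobank". No survey before the intervention is described, so there is no baseline knowledge score to adjust for.

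The same section states: "We will also collect demographic information on the participants". The only use given for these data is in the Analysis Plan: "Summary statistics for baseline demographics (age, ethnicity, race, income, etc.) will be calculated" and reported by group.

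A general sentence in the Analysis Plan promises multilevel mixed models under intention to treat (ITT), but it names no covariates. The Clinical Site Coordination section refers to three sites, yet the knowledge model has no hospital term.

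**The concern.** A knowledge score about consent and biobanking plausibly varies with age, income and social background. If so, a group-only model leaves that variation in the error term. Confidence intervals are then wider and power is lower than the collected data would allow. Without a pre-test, the strongest possible covariate is absent, so the demographics and hospital are the main adjustment variables on hand.

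The documents do not say when the demographics are recorded relative to randomisation. For these particular variables that matters little. A six-minute video or an educational app cannot change a respondent's age, race, ethnicity or income, so adjusting for them does not remove part of the intervention effect.

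**Working it through.** **Inputs from the documents.** Group-only linear model for a composite score; two-sided alpha of 0.05; demographics collected; three sites. The text available for review states no sample size, effect size, standard deviation or power, so there is no figure of the plan's own to reproduce.

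**Inputs assumed.** R2, the share of knowledge-score variance explained by the covariates, from 0 to 0.30. A reference pairwise comparison with 80% unadjusted power, for example 175 per arm at a standardised difference of 0.3.

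**Step 1: gross gain.** Adjustment multiplies the residual variance by (1 − R2).
- Standard error ratio = √(1 − R2).
- Equivalent sample-size factor = 1/(1 − R2).
- Power ≈ Φ(2.80/√(1 − R2) − 1.96), where 2.80 = 1.96 + 0.84 corresponds to 80% power.

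| R2 | SE ratio | SE reduction | Sample-size equivalent | Power (from 80%) | n per arm for 80% power |
|---|---|---|---|---|---|
| 0 | 1.000 | 0% | 0% | 80% | 175 |
| 0.05 | 0.975 | 2.5% | +5.3% | 82% | 166 |
| 0.10 | 0.949 | 5.1% | +11.1% | 84% | 157 |
| 0.20 | 0.894 | 10.6% | +25.0% | 88% | 140 |
| 0.30 | 0.837 | 16.3% | +42.9% | 92% | 123 |

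The SE and sample-size columns do not depend on n or on the effect size. The last two columns depend on the assumed reference design.

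**Step 2: cost of estimating the covariates.** With p covariate parameters and n per arm, the variance is inflated by approximately (2n − 3)/(2n − 3 − p). Adjustment breaks even when R2 = p/(2n − 3).
- n = 100: 5/197 = 0.025; 8/197 = 0.041; 11/197 = 0.056.
- n = 200: 5/397 = 0.013; 8/397 = 0.020.
- n = 300: 5/597 = 0.008; 8/597 = 0.013.

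**Step 3: net effect.** The net variance ratio is (1 − R2) × (2n − 3)/(2n − 3 − p). With n = 100 and p = 8 the inflation is 197/189 = 1.042:
- R2 = 0: 1.042, SE about 2.1% larger (√1.042 = 1.021).
- R2 = 0.05: 0.95 × 1.042 = 0.990, SE about 0.5% smaller.
- R2 = 0.10: 0.90 × 1.042 = 0.938, SE about 3.1% smaller.
- R2 = 0.20: 0.80 × 1.042 = 0.834, SE about 8.7% smaller.
- R2 = 0.30: 0.70 × 1.042 = 0.730, SE about 14.6% smaller.

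With p = 11 and n = 100, R2 = 0.05 gives 0.95 × 197/186 = 1.006, so there is no gain. That count could arise with age (1 term), hospital (2 terms) and 8 terms for finely split race/ethnicity and income.

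**The case against.** The strongest defence is that nothing here is wrong. Randomisation makes the group-only comparison unbiased, its type I error is correct, and a t-test is transparent. That stands in full. A reader might infer that the result is biased or left exposed to chance imbalance, but the documents do not support this. The unadjusted standard error already allows for chance imbalance, so imbalance is not a harm separate from the loss of precision.

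The second objection is that the benefit is hypothetical. This also stands. R2 and the 80% starting power are both assumptions. Entry is limited to English-speaking adults already being approached for the biobank, which may narrow the demographic spread. A reader might take a gain of 5% to 43% in effective sample size as established. That range is gross of degrees-of-freedom cost and leaves out R2 = 0, where there is a small loss.

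Third, adjustment brings complications. Survey Tools does not promise complete demographics for every woman, and self-reported income may be missing. Dropping those participants would conflict with the ITT statement. The Partners section also allows for the respondent to be a partner. These points call for a short rule in the plan; they do not defeat the proposal.

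Two further inferences should be resisted. The absence of a pre-test is not itself the defect, since a pre-test would be a trade-off and is not proposed here. Nor does the text reviewed label knowledge as the primary outcome. It is the first outcome listed and the only one given a model. The text ahead of the Run-in Phase section was not available for review and may hold a sample size or further detail.

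**Conclusion.** The point holds as an inexpensive improvement in precision, not as an error of validity. The specific knowledge model is group-only, and the general mixed-model sentence does not change that. The gain is negligible if the demographics explain about 5% of the variance or less, and worthwhile at 10% to 20%. The 92% power at R2 = 0.30 is an upper illustration with no support in the documents. With a short covariate list and at least 100 per arm, the possible loss is small (about 2% in the standard error at 8 terms and R2 = 0). With a long list it could cancel a modest gain, so the number of terms matters.

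**What to change.** Replace the group-only model in the Analysis Plan with a linear model of knowledge on group plus a short covariate set fixed before the data are examined: age, race/ethnicity and income in few categories, and hospital. To stay within about 8 terms, age (1) and hospital (2) leave 5 for race/ethnicity and income, including any missing category. Use the survey respondent's own characteristics.

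State a simple rule for missing covariates, such as a missing-category indicator or imputation that uses neither group nor outcome, so that no randomised participant is dropped from the ITT analysis. Report the adjusted group contrasts as the main knowledge result and the unadjusted t-test as a sensitivity analysis.

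The cost is a few degrees of freedom, a coding scheme for the categories and the missing-covariate rule: a short paragraph of plan text. It needs no new data, no pre-test and no added burden on participants.
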